## 10.6. Electrocardiogram (ECG)

12-lead ECG including Ventricular Heart Rate (bpm), PR interval (msec), QRS interval (msec), QT interval (msec), QTcF interval (msec), QTcB interval (msec) will be summarized descriptively [REDACTED]

[REDACTED], by treatment, using mean values and mean change from baseline values, as well as numbers of subjects with values outside limits of the normal range at each time point. The overall ECG interpretation (normal, abnormal NCS, abnormal CS) will also be summarized by treatment at each timepoint.

Subject listing of 12-lead ECG will be provided. Subjects with abnormal ECG interpretation will be presented in the listings.

## 10.7. Physical Examination

A complete physical examination (head, eyes, ears, nose, and throat; heart; lungs; abdomen; skin; cervical and axillary lymph nodes; and neurological [mental status, cranial nerve functions, motor and sensory function, cerebellar function, speech, gait] and musculoskeletal systems) will be performed [REDACTED]

Symptom-driven, limited physical examinations and neurological examinations will be performed as clinically indicated [REDACTED].

Subject listings of physical examinations and neurological examinations will be provided. Subjects with abnormal interpretation will be presented in the listings.

## 10.8. Bleeding assessment

Th Bleeding assessment will be done by the Investigator or designee and categorized as sICH and asymptomatic ICH. The occurrence of sICH and asymptomatic ICH within 36 hours and 7 days after dosing will be recorded.

Subject listings of bleeding assessment will be provided.

This document is confidential.

**10.9. Analysis of Primary Safety Endpoint**

The frequency and proportion of symptomatic intracranial hemorrhage (sICH) within 36 hours of dosing will be reported by treatment group and overall. Comparisons by treatment group will be made [REDACTED]

[REDACTED] for the ITT [REDACTED]

**10.10. Occurrence of sICH [REDACTED]**

The frequency and proportion of sICH [REDACTED] will be reported by treatment group and overall. Symptomatic ICH will not be imputed for subjects missing either NIHSS score or CT/MRI examination so the denominator will be the number of subjects in whom sICH could be assessed. Comparisons of treatment group will be made [REDACTED]

[REDACTED]. No formal adjustment for multiple comparisons will be made. [REDACTED]

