9.5 Prior and Concomitant Therapy

9.5.1 Prior and Concomitant Medications

Restricted prior therapies are provided in [Section 8.2](#).

All medications and other treatments taken by the subject during the study, including those treatments initiated before the start of the study, must be recorded on the eCRF.

Medications taken by or administered to the subject for the time period before Screening [REDACTED] will be recorded in the eCRF. After the dosing of investigational product, medication to treat minor treatment-emergent illness(es) is generally permitted. After 24 hours of completion of investigational product infusion, use of antiplatelet agent(s) will be at the discretion of the Investigator. After 24 hours, the following are allowed at the discretion of the Investigator: heparin, non-vitamin K antagonist oral anticoagulant such as dabigatran, rivaroxaban, apixaban, or other factor Xa inhibitors. Low dose heparin or low molecular weight heparin at a preventive dose are allowed from 24 hours after treatment completion and after no intracranial bleeding has been confirmed on 24 hours repeat brain imaging.

[figure not shown]
Any medication or therapy that is taken by or administered to the subject during the course of the study must be recorded in the eCRF. The entry must include the dose, regimen, route, indication, and dates of use.

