14.3.2 Analysis of Secondary Safety Endpoints

14.3.2.1 Occurrence of sICH

The frequency and proportion of sICH [REDACTED] will be reported by treatment group and overall. Symptomatic ICH will not be imputed for subjects missing either NIHSS score or CT/MRI examination so the denominator will be the number of subjects in whom sICH could be assessed. Comparisons of treatment group will be made [REDACTED] no formal adjustment for multiple comparisons will be made.

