## **4. Endpoints**

### **4.1. Primary Endpoint**

[figure not shown]
The primary endpoint of this study is the occurrence of symptomatic intracranial hemorrhage (sICH) within 36 hours after dosing -- clinical deterioration defined as an increase in the National Institute of Health Stroke Scale (NIHSS) of 4 points or more AND confirmed by computed tomography (CT)- or magnetic resonance imaging (MRI)- documented.

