## **6. General Aspects for Statistical Analysis**

### **6.1. General Methods**

- The statistical evaluation will be performed using SAS® software version 9.4 or higher (SAS Institute, Cary, NC). All data will be listed, and summary tables will be provided.
- Summary statistics will be presented by treatment group and overall. For continuous variables, data will be summarized with the number of subjects (N), mean, standard deviation (SD), median, minimum, and maximum by treatment group. For categorical variables, data will be tabulated with the number and proportion of subjects for each category by treatment group.
- The dictionary (MedDRA and WHODrug) version used will be specified in corresponding data display footnote.
- Unless otherwise stated, all listings will include all subjects in ITT Population, and all listings will be sorted by subject ID, treatment, and assessment date/time.
- For all percentage calculations, the denominator will be the number of subjects in the relevant population, unless otherwise stated.
- Only data from protocol scheduled visits will be included in the summary tables. Data from unscheduled visits will not be included in the summary tables but will be included in the listings.

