**10.11. Occurrence of Asymptomatic ICH [REDACTED]**

The frequency and proportion of asymptomatic ICH [REDACTED] will be reported by treatment group and overall. Intracranial hemorrhage will not be imputed for subjects missing either NIHSS score or CT/MRI examination at each visit so the denominator will be the number of subjects in whom ICH could be assessed. Comparisons of treatment group will be made [REDACTED]

[REDACTED]. No formal adjustment for multiple comparisons will be made. [REDACTED]

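### The secondary sICH and asymptomatic ICH rates (SAP 10.10, 10.11) count only subjects with both NIHSS and imaging, so an imaged bleed without NIHSS enters neither rate and some certain non-events are dropped

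*SAP*

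**What the plan says.** SAP 4.1 defines sICH by two conditions that must both hold: "an increase in the National Institute of Health Stroke Scale (NIHSS) of 4 points or more AND confirmed by computed tomography" or MRI.

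SAP 10.10 then sets the rule for the secondary sICH rate. Nothing is imputed for "subjects missing either NIHSS score or CT/MRI examination so the denominator will be the number of subjects in whom sICH could be assessed". SAP 10.11 carries the rule to asymptomatic ICH, visit by visit: "Intracranial hemorrhage will not be imputed for subjects missing either NIHSS score or CT/MRI examination at each visit". The protocol says the same. Section 14.3.2.1 reads "Symptomatic ICH will not be imputed for subjects missing either NIHSS score or CT/MRI examination", and 14.3.2.2 matches SAP 10.11.

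The general rules do not soften this. SAP 6.3 bars imputation, and SAP 6.1 makes the relevant population the default denominator only where nothing else is stated. Sections 10.10 and 10.11 do state something else.

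SAP 10.8 gives a second source of classification: "Bleeding assessment will be done by the Investigator or designee and categorized as sICH and asymptomatic ICH", for 36 hours and for 7 days. What it visibly promises from that source is a listing: "Subject listings of bleeding assessment will be provided".

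The visible endpoint list in SAP 4.2 has no combined any-ICH endpoint. Part of that list is redacted, and the table index is withheld.

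**The concern.** Asking for both measurements is a natural way to decide whether a bleed is symptomatic. It is less suitable as an entry condition for both rates, because the two measurements carry different information. Imaging shows whether there is a bleed; NIHSS only sorts a bleed into symptomatic or asymptomatic. When NIHSS alone is missing, the rule discards what imaging already shows. A proven bleed goes uncounted, and a proven absence of bleeding leaves the denominator.

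Safety is the primary objective and bleeding is its main question. About 16 subjects receive LT3001, so a single case decides whether the table where it belongs shows an event or none.

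**Working it through.** **Inputs.** About 24 subjects at 2:1 (SAP 3.5): 24 × 2/3 = 16 on LT3001 and 24 × 1/3 = 8 on placebo. I assume all are dosed. The documents give no ICH rate, no missingness rate and no power figure, so there is no stated figure to reproduce. All case counts below are assumptions.

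**Step 1: apply the rule to every combination of imaging and NIHSS change.**

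| Imaging | NIHSS rise | In the denominators? | Counted as |
|---|---|---|---|
| positive | 4 or more | yes | sICH |
| positive | under 4 | yes | asymptomatic ICH |
| positive | missing | no | nothing |
| negative | 4 or more | yes | non-event |
| negative | under 4 | yes | non-event |
| negative | missing | no | nothing |
| missing | any of the three | no | nothing |

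Four of the nine combinations are counted and five are excluded. The point concerns the two rows with imaging present and NIHSS missing. The three combinations without imaging are left aside, since without a scan a bleed can be neither shown nor excluded.

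In the negative/missing row the exclusion is unnecessary only if imaging covers the endpoint window. sICH needs imaging confirmation and asymptomatic ICH needs a bleed, so imaging that is negative throughout rules out both.

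**Step 2: size of a lost bleed.** Exact (Clopper-Pearson) 95% limits. With no events the upper limit is 1 − 0.025^(1/n). With x events in n the limits are the 2.5% quantile of Beta(x, n − x + 1) and the 97.5% quantile of Beta(x + 1, n − x).

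| Assumed case | Table where the bleed belongs, if counted | Same table under the rule |
|---|---|---|
| one LT3001 bleed without NIHSS | 1/16 = 6.25% (0.2 to 30.2%) | 0/15, upper limit 21.8% |
| two such bleeds, same table | 2/16 = 12.5% (1.6 to 38.3%) | 0/14, upper limit 23.2% |
| one placebo bleed without NIHSS | 1/8 = 12.5% (0.3 to 52.7%) | 0/7, upper limit 41.0% |
| one such bleed, overall column | 1/24 = 4.2% (0.1 to 21.1%) | 0/23, upper limit 14.8% |

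For the first case: 1 − 0.025^(1/15) = 0.218.

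The other ICH table would have had no event anyway. For one LT3001 case it moves from 0/16 (1 − 0.025^(1/16) = 0.206, upper limit 20.6%) to 0/15 (21.8%).

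**Step 3: size of dropped non-events.** Take one fully assessed LT3001 bleed and k subjects without NIHSS whose negative imaging covers the window. The rate is 1/(16 − k): 6.25% for k = 0, 6.67% for k = 1, 7.14% (0.2 to 33.9%) for k = 2, 8.33% for k = 4. This acts against the effect in step 2.

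**Step 4: how easily NIHSS could be missing.** If each subject independently lacks NIHSS with probability p, the chance that at least one of n does is 1 − (1 − p)^n. For p = 2%, 5% and 10% this is 38%, 71% and 92% with n = 24, and 28%, 56% and 81% with n = 16. These are chances of any missing NIHSS, not of a bleed with NIHSS missing, which also requires a bleed.

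**The case against.** Several counter-arguments carry weight.

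*The wording leaves room.* A negative scan, or a category recorded by the investigator under SAP 10.8, is an observation and needs no imputation, so ICH arguably could be assessed in such subjects. That reading is possible. But the text ties the denominator directly to missing either measurement, and nothing visible lets the investigator's category stand in for a missing NIHSS.

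*The bleed is reported elsewhere.* A reader might infer that it vanishes from the report. It does not. It belongs in the AE and serious TEAE tables (SAP 10.3), in the bleeding listing (10.8) and, if fatal, in the bleeding-mortality table (10.12). This limits the harm but does not correct the two prespecified ICH rates.

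*Both tables lose an event.* A reader might infer this, but a bleed is either symptomatic or asymptomatic, so with complete data it would enter only one table. One event is lost from one table.

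*Any negative scan settles the matter.* It settles only the time it covers. Protocol 9.5.1 refers to the state "after no intracranial bleeding has been confirmed on 24 hours repeat brain imaging"; a 24-hour scan alone does not reach 36 hours or 7 days. The imaging schedule is withheld, so coverage cannot be checked.

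*The primary endpoint is affected.* The visible text of SAP 10.9 and Protocol 14.3.1 does not contain the rule. Both are partly redacted, so extending the point to the primary analysis is not supported.

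*Severe bleeds make NIHSS missing.* The NIHSS form in Protocol Appendix 2 gives scoring instructions for intubated and comatose patients, so severity alone does not cause missingness.

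*Unscheduled data and deaths.* SAP 6.1 says "Data from unscheduled visits will not be included in the summary tables but will be included in the listings", and SAP 8.2.3 labels a score of 42 as dead. A reader might infer that unscheduled scans are barred from the ICH rates, or that deaths are left unscored. The visible text says neither, and redacted text may answer both. Neither is part of this point.

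**Conclusion.** The point holds for the secondary rates in SAP 10.10 and 10.11 and the matching protocol sections. As the visible text reads, an imaged bleed without usable post-dose NIHSS is in neither rate, and a subject with window-long negative imaging but no NIHSS is dropped without need.

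In absolute terms the size is one event per case. In an arm of about 16 that is the difference between reporting an event and reporting none in one table. The net direction cannot be predicted, because the two exclusions oppose each other; the documents do not support a claim of systematic understatement.

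The conclusion rests on arms of 16 and 8, on assumed case counts, and on the redacted ends of 10.10 and 10.11 and the withheld table index not already supplying a supportive analysis. For that last reason confidence is medium. The rule should still be fixed, because the visible text is explicit and the remedy is cheap.

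**What to change.** Leave the primary endpoint definition alone and make three changes to SAP 10.10 and 10.11:

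1. Add an any-ICH-on-imaging row by arm, with a denominator that requires imaging only.
2. Show imaging-proven ICH with NIHSS missing as its own category by arm, with a sensitivity row that counts these cases as sICH.
3. Keep as non-events in both rates those subjects whose imaging is negative and covers the endpoint window, whether or not NIHSS is available.

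Record the departure from Protocol 14.3.2.1 and 14.3.2.2 in SAP section 12. If redacted text already provides any of these rows, a cross-reference is enough.

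The cost is a short SAP revision and a few table rows built from data already collected. The downsides are slightly longer tables and a possibly less favourable reported ICH rate.

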**10.11. Occurrence of Asymptomatic ICH [REDACTED]**

The frequency and proportion of asymptomatic ICH [REDACTED] will be reported by treatment group and overall. Intracranial hemorrhage will not be imputed for subjects missing either NIHSS score or CT/MRI examination at each visit so the denominator will be the number of subjects in whom ICH could be assessed. Comparisons of treatment group will be made [REDACTED]

[REDACTED]. No formal adjustment for multiple comparisons will be made. [REDACTED]

**10.12. Occurrence of Mortality Due to Intracerebral or Other Major Bleeding Complications**

The frequency and proportion of subjects who have died due to intracerebral or other major bleeding complications [REDACTED] will be reported by treatment group and overall. Comparisons by treatment group will be made [REDACTED]

**10.13. Occurrence of Mortality Due to Any Reason [REDACTED]**

The frequency and proportion of subjects who have died due to any reason will be reported [REDACTED] by treatment group and overall. Comparisons of treatment group will be made [REDACTED]

[REDACTED] No formal adjustment for multiple comparisons will be made. [REDACTED]

**10.14. Proportion of Subjects With NIHSS Change from Baseline**

The proportion of subjects with an increase in the NIHSS of  $\geq 4$  points, increase of 1-3 points, no increase/decrease, decrease of 1-3 points and decrease  $\geq 4$  points from Baseline [REDACTED]

[REDACTED]. [REDACTED]

[REDACTED] No formal adjustment for multiple comparisons will be made. [REDACTED]

## **11. Interim Analyses**

No interim analyses are planned.

This document is confidential.

## 12. Changes from Analysis Planned in Protocol

- [REDACTED]
- [REDACTED]
- [REDACTED]
- [REDACTED]
- Update definition of PP population from 'The PP population will comprise all ITT subjects who complete study procedures through Day 90 without a major protocol deviation.' to 'The PP population will comprise all ITT subjects who complete study procedures through Day 90 without a major protocol deviation potentially impacting efficacy measurements.'

This document is confidential.

## **14. Programming Considerations**

All tables, data listings, figures (TFLs), and statistical analyses will be generated using SAS® for Windows, Release 9.4 (SAS® Institute Inc., Cary, NC, USA). Computer-generated table, listing and figure output will adhere to the following specifications.

### **14.1. General Considerations**

- A separate SAS program will be created for each output.
- Each output will be stored in a separate file.
- Output files will be delivered in RTF format.
- Numbering of TFLs will follow ICH E3 guidance

### **14.2. Table, Listing, and Figure Format**

#### **14.2.1. General**

- All TFLs will be produced in landscape format on A4 paper size, unless otherwise specified.
- All TFLs will be produced using the Courier New font, size 8 which is the smallest acceptable point size for the Regulatory Authorities.
- The data displays for all TFLs will have a minimum blank 1-inch margin on all 4 sides.
- Headers and footers for figures will be in Courier New font, size 8 which is the smallest acceptable point size for the Regulatory Authorities.
- Legends will be used for all figures with more than 1 variable, group, or item displayed.
- TFLs will be in black and white (no color), unless otherwise specified
- Specialized text styles, such as bolding, italics, borders, shading, and superscripted and subscripted text, will not be used in the TFLs, unless otherwise specified. On some occasions, superscripts 1, 2, or 3 may be used (see below).
- Only standard keyboard characters will be used in the TFLs. Special characters, such as non-printable control characters, printer-specific, or font-specific characters, will not be used. Hexadecimal-derived characters will be used, where possible, if they are appropriate to help display math symbols (e.g.,  $\mu$ ). Certain subscripts and superscripts (e.g., cm^2, Cmax) will be employed on a case-by-case basis.
- Mixed case will be used for all titles, footnotes, column headers, and programmer-supplied formats, as appropriate.

#### **14.2.2. Headers**

- All output should have the following header at the top left of each page:
- Lumosa Therapeutics Protocol LT3001-201 [REDACTED]

This document is confidential.

- Draft/Final Run <date>
- All output should have Page n of N at the top or bottom right corner of each page. TFLs are internally paginated in relation to the total length (i.e., the page number should appear sequentially as page n of N, where N is the total number of pages in the table).
- The date output was generated should appear along with the program name as a footer on each page.

#### 14.2.3. Display Titles

- EachFL are identified by the designation and a numeral. (i.e., Table 14.1.1). ICH E3 numbering is strongly recommended, but sponsor preferences are obtained before final determination. A decimal system (x.y and x.y.z) are used to identify TFLs with related contents. The title is centered. The analysis set are identified on the line immediately following the title. The title and table designation are single spaced. A solid line spanning the margins will separate the display titles from the
- Column headers. There will be 1 blank line between the last title and the solid line.

Table x.y.z  
First Line of Title  
Second Line of Title if Needed  
(ITT Analysis Set)

#### 14.2.4. Column Headers

- Column headings are displayed immediately below the solid line described above in initial upper-case characters
- In the case of efficacy tables, the variable (or characteristic) column will be on the far left followed by the treatment group columns and total column (if applicable). P-values may be presented under the total column or in separate p-value column (if applicable). Within-treatment comparisons may have p-values presented in a row beneath the summary statistics for that treatment.
- For numeric variables, include “unit” in column or row heading when appropriate.
- Analysis set sizes will be presented for each treatment group in the column heading as (N=xx) (or in the row headings, if applicable). This is distinct from the ‘n’ used for the descriptive statistics representing the number of subjects in the analysis set.
- The order of treatments in the tables and listings will be Placebo first in the case of placebo controlled studies and Active comparators first in the case of active comparator trials, followed by a total column (if applicable).

#### 14.2.5. Body of the Data Display

##### 14.2.5.1. General Conventions

Data in columns of a table or listing are formatted as follows:

- Alphanumeric values are left-justified;

This document is confidential.

- Whole numbers (e.g., counts) are right-justified; and
- Numbers containing fractional portions are decimal aligned.

#### **14.2.5.2. Table Conventions**

- Units will be included where available
- If the categories of a parameter are ordered, then all categories between the maximum and minimum category are presented in the table, even if n=0 for all treatment groups in a given category that is between the minimum and maximum level for that parameter. For example, the frequency distribution for symptom severity would appear as:

Severity Rating	N
severe	0
moderate	8
mild	3

Where percentages are presented in these tables, zero percentages will not be presented and so counts of 0 will be presented as 0 and not as 0 (0%).

- If the categories are not ordered (e.g., Medical History, Reasons for Discontinuation from the Study, etc.), then only those categories for which there is at least 1 subject represented in 1 or more groups are included.
- An Unknown or Missing category are added to each parameter for which information is not available for 1 or more subjects.
- Unless otherwise specified, the estimated mean and median for a set of values are printed out to 1 more significant digit than the original values, and SDs are printed out to 2 more significant digits than the original values. The minimum and maximum should report the same significant digits as the original values. For example, for systolic blood pressure:

N	XX
Mean	XXX.X
Std Dev	X.XX
Median	XXX.X
Minimum	XXX
Maximum	XXX

- P-values are output in the format: "0.xxx", where xxx is the value rounded to 3 decimal places. Every p-value less than 0.001 will be presented as <0.001. If the p-value are less than 0.0001, then present as <0.0001. If the p-value is returned as >0.999, then present as >0.999
- Percentage values are printed to one decimal place, in parentheses with no spaces, one space after the count (e.g., 7 (12.8%), 13 (5.4%)). Pre-determine how to display values that round down to 0.0. A common convention is to display as '<0.1', or as appropriate with additional decimal places. Unless otherwise noted, for all percentages, the number of subjects in the analysis set for

This document is confidential.

the treatment group who have an observation will be the denominator. Percentages after zero counts should not be displayed and percentages equating to 100% are presented as 100%, without decimal places.

- Tabular display of data for medical history, prior/concomitant medications, and all tabular displays of AE data are presented by the body system, treatment class, or SOC with the highest occurrence in the active treatment group in decreasing order, assuming all terms are coded. Within the body system, drug class and SOC, medical history (by PT), drugs (by ATC1 code), and AEs (by PT) are displayed in decreasing order. If incidence for more than 1 term is identical, they should then be sorted alphabetically. Missing descriptive statistics or p-values which cannot be estimated are reported as “-”.
- The percentage of subjects is normally calculated as a proportion of the number of subjects assessed in the relevant treatment group (or overall) for the analysis set presented. However, careful consideration is required in many instances due to the complicated nature of selecting the denominator, usually the appropriate number of subjects exposed. Describe details of this in footnotes or programming notes.
- For categorical summaries (number and percentage of subjects) where a subject can be included in more than one category, describe in a footnote or programming note if the subject are included in the summary statistics for all relevant categories or just 1 category and the criteria for selecting the criteria.
- Where a category with a subheading (such as SOC) has to be split over more than one page, output the subheading followed by “(cont)” at the top of each subsequent page. The overall summary statistics for the subheading should only be output on the first relevant page.

